In studies conducted with children with ADHD, the presence of problems related to sensory processing was determined by both behavioral and neurophysiological measurements. Electroderm In a study conducted with skin responses, it was found that children with ADHD had more sensory reactivity responses than the control group (12). Another study conducted with EEG showed that children with ADHD with tactile sensitivity and children with ADHD without ADHD differ in the processing of somatosensory brain areas (13). Studies evaluating behaviors have revealed results that support these neurophysiological findings. Dunn and Benett's study using the Sensory Profile (DP) family scale revealed that individuals with ADHD differ in all 14 subtest sections of the DP family scale, including hearing, touch, multi-sensory processing, emotional/social responses, and behavioral outcomes (11). In another study conducted with the same scale, individuals with ADHD showed higher sensory reactivity responses than their controls, supporting previous findings (14). Although there are many studies using family scales such as DP, which measures sensory modulation skills in individuals with ADHD, there are limited studies evaluating sensory perception and sensory perception-based problems. In another study, individuals with ADHD had lower scores in the somatosensory perception tests of the DBPT when compared to the healthy group, and it was revealed that these individuals had a weak tactile and proprioceptive perception (13).

Although there are studies in the literature showing the presence of DDD in children with ADHD, most researchers have studied a similar profile, such as sensory modulation disorder, and few have investigated all components of sensory integration (such as sensory perception, praxis) (17). More research is needed to confirm the effects of Ayres Sensory Integration therapy in children with ADHD and the possible relationship between DDD-based difficulties in activities of daily living and ADHD symptoms. In our study, it was aimed to investigate the effect of Ayres Sensory Integration therapy on sensory, motor, cognitive, behavioral and social participation in children with ADHD in the light of extensive literature and recommendations.

3. Benefits and Risks Expected from Study

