The evaluations to be made within the scope of the study do not involve any risk. At every moment of Ayres Sensory Integration Therapy applications, there will be at least one researcher, including our volunteer child and their parents. Considering all this information, participation in our study does not pose a risk. Difficulty with sensory and motor skills is a common problem for children with attention deficit hyperactivity disorder. With a structured sensory integration therapy application, it is aimed to reduce the sensory, motor and cognitive difficulties of children in their daily lives.

4. Materials and Methods

4.1. Study Place:

In this research, PhD student [name], [name] [name], [name]. [name] and [name]. [name] will take part in the evaluation, data analysis and writing stages. The research will take place in the pediatric rehabilitation unit of Hacettepe University, Department of Occupational Therapy.

4.2. Time to Study:

The study is planned to be completed between February 2023 and April 2024, starting immediately after the approval of the ethics committee.

4.3. Study Population, Sample, Research Group:

Study group and control group will be compared in the research. The change between the last evaluation and the first evaluation will be calculated and a comparison of this change between the two groups will be made. T-test will be used in independent groups for this comparison. The effect size was predicted to be 0.8. With 5% margin of error and 80% power, the sample size was calculated as (45 + 45) 90 for the groups. Participants will be divided into two groups as training group and control group. All volunteering children will be included in the study, taking into account the inclusion and exclusion criteria.

Inclusion criteria:

- a. To be in the age range of 6-8,
- b. Being diagnosed with Attention Deficit Hyperactivity Disorder according to the DSM-V criteria,
- c. Continuing school education,
- d. Having agreed to participate in the study after being informed about the research.

Exclusion criteria:

Children with additional physical and neurological problems will be excluded from the study.

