4.4. Type of Study: Randomized Controlled Trial

The simple randomization method will be used in this study, and volunteers will be divided into study and control groups at random and with equal probability, taking into account the inclusion and exclusion criteria. For simple randomization, block randomization method will be used.

4.5. Required Manpower for Research:

[name] [name] and [name]. [name] will diagnose patients and direct them for research. The first and second evaluations were blinded by [name]. [name] will be made Ayres Sensory Integration Therapy be implemented by [name]. [name] has a Ayres Sensory Integration Therapy Practitioner Certificate.

4.6. Data Collection Tools of the Research:

Sociodemographic Information Form

Participants' age, gender, time of diagnosis, number of siblings, parental education and employment status, etc. sociodemographic information form which contains the information will be used.

Sensory Profile (SP)

The Sensory Profile (SP) is a family-reported scale that provides data on children's reactions to sensory events in daily life, how sensory behaviors can contribute to performance in daily life, and what difficulties they cause in performance. It consists of 125 questions that can be applied between the ages of 3-10 (18). It has been found that SP effectively distinguishes between typically developing children and children with various developmental difficulties (19). Turkish adaptation study was done by Kayıhan et al. (20).

Sensory Integration and Praxis Test (SIPT)

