The Sensory Integration and Praxis Test (SIPT), developed by Ayres, is a standardized performance-based observational test that evaluates sensory perception and sensory perception-based skills in detail in children between the ages of 4 and 8 years and 11 months (21). SIPT is one of the important gold tests in evaluating sensory development and consists of 17 subtests. These subtests provide information on visuospatial perception, visual discrimination, tactile perception, kinesthesia, following verbal instructions, visual motor planning, imitation of body and mouth movements, balance, bilateral coordination, sequencing of movements, and vestibular processing. There is no Turkish reliability and validity study of this test, which evaluates the child's performance, but it is applied by therapists who have international certification in this regard in our country. On the other hand, some studies have suggested that cultural differences do not affect SIPT

scores (22, 23). In our study, it was decided to use SIPT to compare pre-intervention and post-intervention sensory development scores.

Emotion Regulation Checklist (ERC)

The Emotion Regulation Checklist (ERC) is a 24-item scale developed by Shields and Cicchetti to evaluate the emotion regulation competence of children aged 6-13 and can be evaluated by both parents and teachers (24). The items of the scale evaluate affect lability/negativity and emotion adjustment with the items changing on the plot of "never" and "almost always" on a 4-point Likert scale. Its Turkish adaptation was made by Gül Kapçı et al. (25).

Stroop Test TBAG Form (Stroop TBAG)

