intervention. It provides the child's continuous interest in the set goals and offers a person-centered approach (39). The determined goals should be specific, measurable, achievable, relevant and well-timed (40). While applying GAS, goals are set for the child and possible outcomes are defined for each goal. After a certain intervention, the functional status of the child is determined again. GAS consists of 5 points as -2, -1, 0, +1 and +2. A score of -2 indicates the child's pre-intervention baseline level, a score of -1 indicates a development below the expected attainment level, a score of 0 indicates an expected attainment level, a score of +1 indicates a better-than-expected achievement, and a score of +2 indicates that the child performs much better than expected (39, 40).

4.7. Collection of Data:

The data will be collected by the occupational therapist from the volunteer participants by face-to-face interview method, and consent and evaluation forms will be collected.

4.8. Intervention Program:

Individuals will be interviewed for the Informed Consent Form. Consent will be obtained from each individual who volunteers to participate in the study. Consent forms will be given in writing and will be requested back once signed.

Participants signing the Informed Consent Form will form the working group, taking into account the inclusion and exclusion criteria. This study group will be divided into two as training and control groups by simple randomization method. After the training and control groups are determined as a result of randomization, an initial evaluation will be made for all participants separately. Ayres Sensory Integration Therapy will be applied to the training group for 10 weeks, 3 days a week (30 sessions), 60 minutes per session. Final assessments will be made at week 11 of therapy. In the control group; An appointment will be made 10 weeks after the initial assessment. After 10 weeks, final evaluations will be made for control. After the final evaluation, 30 sessions of Ayres Sensory Integration Therapy will be applied for 10 weeks, 3 days a week, similar to the control group. In the Ayres Sensory Integration Therapy application, the therapist will provide interviews with the child and their parents in structured environments, and the parents will be asked to repeat the session by explaining the goals in an explanatory way after the session.

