[figure not shown]
As descriptive statistics in the study; Frequency (n) and percentage (%) values will be used in the evaluation of categorical variables. Shapiro-Wilk and Kolmogorov-Smirnov normality tests will be used for the conformity of numerical variables to the normal distribution, and as descriptive statistics; Mean±standard deviation values will be given for the variables suitable for normal distribution, and median (minimum-maximum) values will be given for those that do not comply with the normal distribution. The appropriate hypothesis testing method planned to be used in the study was determined as "Two-Way Analysis of Variance with Repetitions on a Single Factor" when parametric test assumptions were met. If the parametric test assumptions for the relevant test are not met, whether there is a difference between the groups in terms of quantitative variables, with the "Student t test" when the parametric test assumptions are met, and with the "Mann-Whitney test" if they are not; In examining whether quantitative variables change according to three separate evaluation times, "Repeated measures variance analysis" will be used when the test assumptions are met, and "Friedman test" if it is not provided. Type I error probability will be taken as $\alpha=0.05$ in all hypothesis tests and SPSS v25.0 package program will be used for statistical evaluations. While calculating the sample size required to test the research hypothesis, the effect widths defined by Cohen* were used and the calculations were made with the G*Power 3.1.9 program.

The minimum sample size required for the study is 90 people in total, approximately equally distributed in the groups that will provide 90% test power at 95% confidence level, with the effect width $f=0.30^*$ for "Two-Way Analysis of Variance in Repeated Measurements with Repetitions on a Single Factor".

F tests - ANOVA: Repeated measures, between factors

Analysis: A priori: Compute required sample size

Input:	Effect size f	=	0,3
	α err prob	=	0,05
	Power ($1-\beta$ err prob)	=	0,9
	Number of groups	=	2
	Number of measurements	=	2
	Corr among rep measures	=	0,5
Output:	Noncentrality parameter λ	=	10,8000000
	Critical F	=	3,9493210
	Numerator df	=	1,0000000
	Denominator df	=	88,0000000
	Total sample size	=	90
	Actual power	=	0,9015268

6. Bibliography

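### The available text names no primary outcome and no multiplicity rule, yet gives every test on at least ten unranked instruments the full 0.05; the stated 90% power is not the power of the planned comparison of change

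*Combined protocol and SAP*

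**What the plan says.** The aim, at the end of the background, is broad: "it was aimed to investigate the effect of Ayres Sensory Integration therapy on sensory, motor, cognitive, behavioral and social participation in children with ADHD". The domains are not ranked.

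Section 4.6 describes ten outcome instruments besides the sociodemographic form: SP, SIPT, ERC, Stroop TBAG, CHEXI, PEM-CY, CTRS, CPRS, BOT-2 and GAS. None is called primary or secondary. The SIPT entry comes nearest to a choice of outcome, since it says SIPT was selected for comparing scores before and after the intervention. It does not rank SIPT above the rest, and SIPT has 17 subtests.

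Section 4.3 gives the comparison: the change from first to last evaluation is calculated, and "a comparison of this change between the two groups will be made" with an independent-groups t test. The sizing there reads "The effect size was predicted to be 0.8" and "With 5% margin of error and 80% power, the sample size was calculated as (45 + 45) 90 for the groups". No score is named.

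Section 5 names a two-way analysis of variance with repetition on one factor, with fallback tests, and states that "Type I error probability will be taken as $\alpha=0.05$ in all hypothesis tests". It gives no adjustment, order or gatekeeping. It also justifies 90 children differently: f = 0.30 and 90% power, with G*Power output for the between-factors procedure (2 groups, 2 measurements, correlation 0.5). Again no score is named.

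**The concern.** A randomised trial sized to test a research hypothesis needs one result that answers it. Here ten instruments stand side by side, each tested at the full 0.05. If therapy had no effect on any of them, a chance difference on one could still be reported with the same standing as any other result, and nothing written in advance would say whether it was the result that counted.

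The sample-size text does not settle the matter. Neither calculation is tied to a score, and the one that claims 90% power uses a procedure that does not test change. So no stated power figure belongs both to a named score and to the comparison the protocol plans.

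**Working it through.** **1. The plan's own figure (section 5).** For the between-factors effect, λ = f² × N × m / (1 + (m − 1)ρ), with f = 0.30, N = 90, m = 2 and ρ = 0.5:

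λ = 0.09 × 90 × 2 / 1.5 = 10.8, on 1 and 88 degrees of freedom, critical F 3.949, power 0.9015.

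This matches the printed output exactly. The effect tested is the group difference averaged over both measurements, baseline included.

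**2. Error rate over ten instruments.** Inputs: α = 0.05 per test (section 5) and ten instruments (section 4.6). Assumptions not in the documents: one two-sided between-group test per instrument, no true effects, and one common correlation r between the test statistics. The 0.5 in the G*Power input is a correlation between time points, not between instruments.

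- Independent tests: 1 − 0.95¹⁰ = 0.401.
- Correlated tests: 1 − E[P(|Z| < 1.96 given U)¹⁰], where U is a shared standard normal factor, by numerical integration.

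| Tests | r = 0 | r = 0.5 | r = 0.7 | r = 0.9 |
|---|---|---|---|---|
| 10 | 40.1% | 28.7% | 21.3% | 12.8% |
| 30 | 78.5% | 50.7% | 33.9% | 17.2% |

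A simulation of ten t tests with 45 per group (20,000 runs per correlation) gives 40.2%, 29.2%, 21.0% and 12.9% for the first row.

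The second row shows why ten is a minimum. Section 4.6 lists 17 SIPT subtests, 5 Stroop sections, 4 CHEXI subgroups and 8 BOT-2 subtests, which is 34 parts in four instruments alone. The plan does not say which of these will be tested.

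**3. Power for the comparison in section 4.3.** For two groups f = 0.30 corresponds to a difference of 2 × 0.30 = 0.6 SD. As an example, let that difference appear only at the final assessment, with equal SDs and 45 + 45 children. The base term is (45/2) × 0.6² = 8.1.

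- Unadjusted change, λ = 8.1 / (2(1 − ρ)): at ρ = 0.5, λ = 8.1 and power is 0.804; at ρ = 0.3 it is 0.662, and at ρ = 0.7 it is 0.953.
- Final score adjusted for baseline, λ = 8.1 / (1 − ρ²): at ρ = 0.5, λ = 10.8 and power is 0.901; at ρ = 0.3 it is 0.839, and at ρ = 0.7 it is 0.976.
- Between-factors effect: the averaged difference is 0.3 SD, so λ = (45/2) × 0.3² / ((1 + ρ)/2). At ρ = 0.5, λ = 2.7 and power is 0.369.

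The 90% in section 5 therefore does not carry over to the t test of change.

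**4. The inputs in section 4.3.** Reading 0.8 as Cohen's d, a two-sided t test at 0.05 has power 0.791 with 25 per group and 0.807 with 26, so 80% needs 26 per group. With 45 per group the power is 0.964. The stated inputs do not lead to 45.

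**The case against.** The strongest reply concerns what could not be read. Section 5 speaks of a single research hypothesis, and the opening of the document, where one might be stated, was not available. A reader might infer that the trial has no primary outcome at all; the documents do not support that. What can be said is that section 5, where the outcome and error rule should appear, contains neither, and that a primary outcome named elsewhere would need to be carried into it.

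A reader might also infer that the comparison itself is undefined. It is not: section 4.3 gives it, and with two measurements the group-by-time term of the ANOVA in section 5 is the same test. The conflict lies in the procedure used for sizing.

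It can fairly be said that the plan nowhere declares success on any single significant instrument, so 40% is not the trial's error rate. That stands, and the figures are an illustration. But the plan states no other decision rule, and it does not call itself exploratory. Correlation between instruments would lower the figure, yet even at 0.9 it is about two and a half times 5%.

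Finally, a reader might conclude that keeping 90% power requires more children. That would follow only for an unadjusted change score. In the example above, adjusting the final score for baseline gives about 90% with 45 + 45.

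**Conclusion.** The point holds, limited to the available text. No primary outcome and no multiplicity rule is given, while 0.05 applies to every test across at least ten unranked instruments. Under the stated assumptions (one test each, no true effects, equal correlation, which the documents do not give), the chance of at least one false-positive difference is 40% at correlation 0, 29% at 0.5, 21% at 0.7 and 13% at 0.9, against 5% for a single test. With 30 tests it would be 79% at 0 and 34% at 0.7.

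The planned comparison of change is stated, but the 90% power is for a different effect, and the inputs in section 4.3 give 26 per group, not 45. The documents do not show that 90 children are too few; they show that the power for the decisive test has not been stated. Confidence is medium because of the unavailable parts. The gap should be closed before analysis.

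**What to change.** Before any outcome data are analysed:

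1. Name one primary score in section 5 and test its between-group comparison alone at two-sided 0.05. If a primary outcome is already named in a part not available to this review, carry it over. If the chosen instrument has subtests, say which score is meant.
2. Report all other instruments as secondary or exploratory, with confidence intervals and no confirmatory claim. If analysis has already begun, label all results exploratory.
3. Restate the power of N = 90 for the named comparison, saying whether change is unadjusted or the final score is adjusted for baseline, and reconcile section 4.3 (0.8, 80%, 45 + 45) with section 5 (f = 0.30, 90%).

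The cost is protocol and SAP wording plus one power calculation, with no extra procedures. In the example above (ρ = 0.5), the baseline-adjusted analysis keeps about 90% power without added enrolment. The downside is that secondary results lose confirmatory standing and the restated power may be below 90%: in the same example, about 80% for unadjusted change, and 84% for the adjusted score if the correlation is 0.3.

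### The printed 90% power is for the group difference averaged over both evaluations, not for the comparison of change, and section 4.3's own 0.8 / 80% / 45 + 45 does not reproduce

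*Combined protocol and SAP*

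**What the plan says.** The plan justifies the same 90 children twice.

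- **Section 4.3 (Study Population, Sample, Research Group).** Change between first and last evaluation is calculated for each child, and "a comparison of this change between the two groups will be made". The test is named: "T-test will be used in independent groups for this comparison". The planning values are also given: "The effect size was predicted to be 0.8" and "With 5% margin of error and 80% power, the sample size was calculated as (45 + 45) 90 for the groups".
- **Section 5 (Statistical Analysis of Data).** The main analysis is a two-way ANOVA with repeated measures on one factor. The 90 children are described as the minimum "that will provide 90% test power at 95% confidence level" at f = 0.30. The pasted G*Power output is headed "F tests - ANOVA: Repeated measures, between factors" and uses 2 groups, 2 measurements and a correlation of 0.5. It prints a noncentrality of 10.8, a critical F of 3.949 on 1 and 88 df, a total of 90 and an actual power of 0.9015.

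Section 5 does not say which term of the ANOVA (group, time or group by time) tests efficacy.

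**The concern.** With two evaluations, a t-test on change and the group-by-time term of the repeated-measures ANOVA are the same test. The procedure used in section 5 is for a different term, the group main effect, which compares the groups on the mean of the two evaluations. The initial evaluation precedes therapy in randomised groups, so no initial difference is expected and the averaging dilutes any benefit by half.

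Two things are at stake. First, the stated power does not belong to the planned comparison, and the two sections give different effect sizes and powers for one sample size. A reader is not told what difference in change the trial was designed to detect. Second, section 5 leaves the efficacy term unnamed, and its output points the analyst to the group main effect. If that term were reported as the efficacy result, a real benefit would often be missed.

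**Working it through.** **Inputs from the plan.** N = 90 (45 per group) and alpha 0.05 (sections 4.3 and 5); f = 0.30, m = 2 measurements and correlation ρ = 0.5 (section 5); effect 0.8 and 80% power (section 4.3). **Assumptions.** Two-sided testing, no expected initial difference, equal SD at both evaluations. The plan gives no source for ρ = 0.5, so 0.3 to 0.7 is also shown. The final difference d is in SDs of the raw score.

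**Step 1: reproduce the section 5 output.** For the group main effect, λ = f²·N·m / (1 + (m − 1)ρ) = 0.09 × 90 × 2 / 1.5 = 10.8. The critical F(1, 88) is 3.9493 and power is 0.9015, exactly as printed. N = 88 gives 89.5%, so 90 is the minimum for this test. The group-by-time formula, λ = f²·N·m / (1 − ρ), would give 0.09 × 90 × 2 / 0.5 = 32.4. The printed λ therefore confirms that the main effect was used and that the heading is not a labelling slip.

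**Step 2: what that 90% requires.** For two groups, f = 0.30 is a difference of 2 × 0.30 = 0.60 SD in the average of the two evaluations. With no initial difference, the average carries half of the final difference, so the final difference must be 2 × 0.60 = 1.20 SD. For ρ from 0.3 to 0.7, the final difference needed for 90% is 1.11 to 1.27 SD.

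**Step 3: power of the two tests for the same final difference d, N = 90.**

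- Main effect: f = d/4, so λ = (d/4)² × 90 × 2 / (1 + ρ).
- Change: λ = d² / (2(1 − ρ)) × 90/4.

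| d (ρ = 0.5) | λ, main effect | Power | λ, change | Power |
|---|---|---|---|---|
| 0.60 | 2.70 | 37% | 8.10 | 80% |
| 0.80 | 4.80 | 58% | 14.4 | 96% |
| 1.20 | 10.80 | 90% | 32.4 | 99.99% |

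At d = 0.60, moving ρ from 0.3 to 0.7 takes the main effect from 42% down to 33% and change from 66% up to 95%. Change reaches 90% at ρ of about 0.62. Simulation with 10,000 runs at d = 0.60 and ρ = 0.5 gave 37.1% and 79.8%.

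**Step 4: can f = 0.30 be read as the interaction effect?** Then N = 32 gives λ = 0.09 × 32 × 2 / 0.5 = 11.52 and 90.7% power, and N = 90 gives more than 99.9%. On that reading 90 does not follow either.

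**Step 5: section 4.3 on its own terms.** For a two-sided t-test on change with a standardised difference of 0.8, 25 per group gives 79.1% and 26 gives 80.7%. The stated 45 per group gives 96.4%. Other settings at 0.8 also miss 45:

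- one-sided, 80% power: 21 per group;
- two-sided, 90% power: 34;
- two-sided, 95% power: 42;
- Mann-Whitney inflation of 26: about 27 to 30.

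Reaching 45 from 26 by dropout would need 1 − 26/45 = 42% loss, and no dropout allowance is stated. If 0.8 is in raw-score SDs, 45 per group gives 89% to 99.8% for ρ of 0.3 to 0.7. An effect of 0.60 does give 45 per group (80.4%), so 0.8 may be a slip; that is inference.

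**Step 6: what 45 per group can detect.** For a t-test on change, the detectable difference is 0.597 SD of change at 80% power and 0.691 at 90%. At ρ = 0.5 the SD of change, √(2(1 − ρ)) times the raw SD, equals the raw SD, so the same figures hold on the raw scale.

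**The case against.** The strongest reply is that little harm follows. Section 4.3 already names the comparison of change, and nothing in section 5 says the main effect will be the efficacy result. From 45 per group and a t-test on change, a reader can work out 0.60 SD of change at 80% without any correlation. Both stated effects, read on change, are covered by 90 children: 0.8 at 80% needs 52, and f = 0.30 as an interaction needs 32 for 90%. The only less favourable reading, 0.60 SD with 80% rather than 90%, rests on converting f to d = 2f, which is our assumption.

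Much of this stands. The sample is not shown to be too small, and the harm from reporting the main effect is conditional. But having to work out the detectable difference is itself the defect, because the plan's own statements give two other answers. Neither the mismatch of test and question nor the 26-versus-45 failure depends on d = 2f.

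One exception is fair. On the Goal Attainment Scale, -2 is defined as the "pre-intervention baseline level, a score of -1 indicates a development below the expected attainment level". With a constant baseline, the average and the change carry the same information, the two tests coincide and ρ is undefined. The halving and the 37%-versus-80% contrast do not apply to that scale.

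**Conclusion.** The concern holds. The section 5 figure is computed correctly, but for a term that is not the treatment comparison in section 4.3. The section 4.3 figure is for the right comparison but does not reproduce. Neither stated pair of effect size and power matches the comparison of change with 90 children.

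The size of the mismatch is a required final difference of 1.20 SD for the printed 90%, against 0.69 SD for 90% on change. This rests on two-sided 0.05, no expected initial difference and ρ = 0.5. The 26 per group for an effect of 0.8 needs no correlation if 0.8 is a standardised difference in change. This should be fixed before analysis. It is a fault in the justification and in the naming of the test, not a case for more children.

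**What to change.** 1. **Replace the section 5 output** with a calculation for the comparison of change, and give the same effect size and power in sections 4.3 and 5. Possible wording: *With 45 children per group, two-sided alpha 0.05 and a correlation of 0.5 between evaluations, the comparison of change has 80% power for a difference of 0.60 SD of the raw score (90% for 0.69 SD, 96% for 0.80 SD).* Say which effect is the planning value and why, and show the result for correlations of 0.3 to 0.7.
2. **Name the test.** State that the group-by-time term, not the group main effect, is the test of efficacy, and that the Mann-Whitney fallback is applied to change scores. Reconcile the three evaluation times mentioned in section 5 with the two measurements entered, because change equals the interaction only with two.
3. **Optional and separate:** analyse the final score by ANCOVA with the initial score as covariate. With λ = d²/(1 − ρ²) × 90/4 on 1 and 87 df, power at 0.60 SD is about 90% at ρ = 0.5, 87% at 0.4 and 84% at 0.3. This does not apply to the Goal Attainment Scale. Section 4.8 also says "After the training and control groups are determined as a result of randomization, an initial evaluation will be made for all participants separately", so the covariate should be measured before allocation is disclosed, or this limit stated.

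Items 1 and 2 cost rewording in two sections and one power calculation, with no extra children or visits. Item 3 adds one covariate in SPSS.
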